#### **11.1.5. Data Protection**

All parties will comply with all applicable laws, including laws regarding the implementation of organizational and technical measures to ensure protection of participant data.

Participant's personal data will be stored at the study site in encrypted electronic and/or paper form and will be password protected or secured in a locked room to ensure that only authorized study staff have access. The study site will implement appropriate technical and organizational measures to ensure that the personal data can be recovered in the event of disaster. In the event of a potential personal data breach, the study site will be responsible for determining whether a personal data breach has in fact occurred and, if so, providing breach notifications as required by law.

To protect the rights and freedoms of participants with regard to the processing of personal data, participants will be assigned a single, participant-specific numerical code. Any participant records or data sets that are transferred to the Sponsor will contain the numerical code; participant names will not be transferred. All other identifiable data transferred to the Sponsor will be identified by this single, participant-specific code. The study site will maintain a confidential list of participants who participated in the study, linking each participant's numerical code to their actual identity and medical record ID. In case of data transfer, the Sponsor will protect the confidentiality of participant's personal data consistent with the clinical study agreement and applicable privacy laws.

Information technology systems used to collect, process, and store study-related data are secured by technical and organizational security measures designed to protect such data against accidental or unlawful loss, alteration, or unauthorized disclosure or access.

The Sponsor maintains standard operating procedures on how to respond in the event of unauthorized access, use, or disclosure of Sponsor information or systems.

#### **11.1.6. Dissemination of Clinical Study Data**

The Sponsor fulfills its commitment to publicly disclose clinical study results through posting the results of studies on [www.clinicaltrials.gov](http://www.clinicaltrials.gov) (ClinicalTrials.gov), the EudraCT/CTIS, and/or [www.pfizer.com](http://www.pfizer.com), and other public registries and websites in accordance with applicable local laws/regulation. In addition, the Sponsor reports study results outside of the requirement of local laws/regulations pursuant to its standard operating procedures.

In all cases, study results are reported by the Sponsor in an objective, accurate, balanced, and complete manner and are reported regardless of the outcome of the study or the country in which the study was conducted.

[www.clinicaltrials.gov](http://www.clinicaltrials.gov)

The Sponsor posts clinical trial results on [www.clinicaltrials.gov](http://www.clinicaltrials.gov) for GBT/Pfizer-sponsored interventional studies (conducted in patients) that evaluate the safety and/or efficacy of a product, regardless of the geographical location in which the study is conducted. These results are submitted for posting in accordance with the format and timelines set forth by US law.

EudraCT/CTIS

The Sponsor posts clinical trial results on EudraCT/CTIS for GBT/Pfizer-sponsored interventional studies in accordance with the format and timelines set forth by EU requirements.

[www.pfizer.com](http://www.pfizer.com)

The Sponsor posts clinical study report (CSR) synopses and plain-language study results summaries on [www.pfizer.com](http://www.pfizer.com) for GBT/Pfizer-sponsored interventional studies at the same time the corresponding study results are posted to [www.clinicaltrials.gov](http://www.clinicaltrials.gov). CSR synopses will have personally identifiable information anonymized.

Documents within marketing applications

The Sponsor complies with applicable local laws/regulations to publish clinical documents included in marketing applications. Clinical documents include summary documents and CSRs including the protocol and protocol amendments, sample CRFs, and SAPs. Clinical documents will have personally identifiable information anonymized.

Data sharing

The Sponsor provides researchers secure access to participant-level data or full CSRs for the purposes of “bona-fide scientific research” that contributes to the scientific understanding of the disease, target, or compound class. The Sponsor will make data from these trials available 18 months after study completion. Participant-level data will be anonymized in accordance with applicable privacy laws and regulations. CSRs will have personally identifiable information anonymized.

Data requests are considered from qualified researchers with the appropriate competencies to perform the proposed analyses. Research teams must include a biostatistician. Data will not be provided to applicants with significant conflicts of interest, including individuals requesting access for commercial/competitive or legal purposes.

**11.1.7. Data Quality Assurance**

All participant data relating to the study will be recorded on printed or electronic CRF unless transmitted to the Sponsor or designee electronically (eg, laboratory data). The Investigator is responsible for verifying that data entries are accurate and correct by physically or electronically signing the CRF.

Guidance on completion of CRFs will be provided in the CRF Completion Requirement document.

The Investigator must ensure that the CRFs are securely stored at the study site in encrypted electronic and/or paper form and are password-protected or secured in a locked room to prevent access by unauthorized third parties.

Quality tolerance limits (QTLs) are predefined parameters that are monitored during the study. Important deviations from the QTLs and any remedial actions taken will be summarized in the CSR.

The Investigator must permit study-related monitoring, audits, IRB/EC review, and regulatory agency inspections and provide direct access to source records and documents. This verification may also occur after study completion. It is important that the Investigator(s) and their relevant personnel are available during the monitoring visits and possible audits or inspections and that sufficient time is devoted to the process.

Monitoring details describing strategy, including definition of study-critical data items and processes (eg, risk-based initiatives in operations and quality such as risk management and mitigation strategies and analytical risk-based monitoring), methods, responsibilities, and requirements, including handling of noncompliance issues and monitoring techniques (central, virtual, or on-site monitoring), are provided in the data management plan maintained and utilized by the Sponsor or designee.

The Sponsor or designee is responsible for the data management of this study, including quality checking of the data.

Records and documents, including signed ICFs, pertaining to the conduct of this study must be retained by the Investigator for 15 years after study completion unless local regulations or institutional policies require a longer retention period. No records may be destroyed during the retention period without the written approval of the sponsor. No records may be transferred to another location or party without written notification to the Sponsor. The Investigator must ensure that the records continue to be stored securely for as long as they are maintained.

When participant data are to be deleted, the Investigator will ensure that all copies of such data are promptly and irrevocably deleted from all systems.

The Investigator(s) will notify the Sponsor or its agents immediately of any regulatory inspection notification in relation to the study. Furthermore, the Investigator will cooperate with the Sponsor or its agents to prepare the Investigator site for the inspection and will allow the Sponsor or its agent, whenever feasible, to be present during the inspection. The Investigator site and Investigator will promptly resolve any discrepancies that are identified between the study data and the participant's medical records. The Investigator will promptly provide copies of the inspection findings to the Sponsor or its agent. Before response submission to the regulatory authorities, the Investigator will provide the Sponsor or its agents with an opportunity to review and comment on responses to any such findings.

#### **11.1.8. Study and Site Start and Closure**

The study start date is the date of the first participant's first visit.

The Sponsor designee reserves the right to close the study site or terminate the study at any time for any reason at the sole discretion of the Sponsor, including (but not limited to)

regulatory authority decision, change in opinion of the IRB/EC, or change in benefit-risk assessment. Study sites will be closed upon study completion. A study site is considered closed when all required documents and study supplies have been collected and a study-site closure visit has been performed.

The Investigator may initiate study-site closure at any time upon notification to the Sponsor or designee/CRO if requested to do so by the responsible IRB/EC or if such termination is required to protect the health of study participants.

Reasons for the early closure of a study site by the Sponsor may include but are not limited to:

- Failure of the Investigator to comply with the protocol, the requirements of the IRB/EC or local health authorities, the Sponsor's procedures, or the ICH GCP guidelines;
- Inadequate recruitment of participants by the Investigator;
- Discontinuation of further study intervention development.

If the study is prematurely terminated or suspended, the Sponsor shall promptly inform the Investigators, the ECs/IRBs, the regulatory authorities, and any CRO(s) used in the study of the reason for termination or suspension, as specified by the applicable regulatory requirements. The Investigator shall promptly inform the participant and should assure appropriate participant therapy and/or follow-up.

Study termination is also provided for in the clinical study agreement. If there is any conflict between the contract and this protocol, the contract will control as to termination rights.

#### **11.1.9. Publication Policy**

For multicenter trials, the primary publication will be a joint publication developed by the Investigator and the Sponsor reporting the primary endpoint(s) of the study covering all study sites. The Investigator agrees to refer to the primary publication in any subsequent publications. The Sponsor will not provide any financial compensation for the Investigator's participation in the preparation of the primary congress abstract, poster, presentation, or primary manuscript for the study.

Investigators are free to publish individual center results that they deem to be clinically meaningful after publication of the overall results of the study or 12 months after primary completion date or study completion at all sites, whichever occurs first, subject to the other requirements described in this section.

The Investigator will provide the Sponsor an opportunity to review any proposed publication or any other type of disclosure of the study results (collectively, "publication") before it is submitted or otherwise disclosed and will submit all publications to the Sponsor 30 days before submission. If any patent action is required to protect intellectual property rights, the Investigator agrees to delay the disclosure for a period not to exceed an additional 60 days upon request from the Sponsor. This allows the Sponsor to protect proprietary information and to provide comments, and the Investigator will, on request, remove any previously undisclosed confidential information before disclosure, except for any study-intervention or

Sponsor-related information necessary for the appropriate scientific presentation or understanding of the study results. For joint publications, should there be disagreement regarding interpretation and/or presentation of specific analysis results, resolution of, and responsibility for, such disagreements will be the collective responsibility of all authors of the publication.

For all publications relating to the study, the investigator and the Sponsor will comply with recognized ethical standards concerning publications and authorship, including those established by the International Committee of Medical Journal Editors. The Investigator will disclose any relationship with the Sponsor and any relevant potential conflicts of interest, including any financial or personal relationship with the Sponsor, in any publications. All authors will have access to the relevant statistical tables, figures, and reports (in their original format) required to develop the publication.

#### **11.1.10. Sponsor's Medically Qualified Individual**

The Sponsor will designate a medically qualified individual (MQI, also known as the medical monitor) to advise the investigator on study-related medical questions. The contact information for the study medical monitor is documented in the Study Team Contact List located in the Investigator Site File.

Participants are provided with a Pfizer study information card at the time of informed consent which includes contact information for their investigator in case of study-related medical questions. The study information card contains, at a minimum, (a) study number, (b) participant's study identification number, and (c) principal investigator contact information.

## 11.2. Supporting Documentation

### 11.3. Appendix 1: Detailed Dosing Information For Osivelotor

#### Dose for Participants Enrolling from Part A of C5351004

**Table 13. Dose for Participants Enrolled Directly from Part A of C5351004**

Maintenance Dose in Part A of C5351004	Maintenance Dose in C5351005 a
100 mg QD	Stay at 100 mg QD
	Increase to 150 mg QD
150 mg QD	Stay at 150 mg QD
	Decrease to 100 mg QD
Up to 200 mg QD	Stay at up to 200 mg QD
	Decrease to 150 mg QD
	Decrease to 100 mg QD

Abbreviations: QD, once daily.

a Until the analysis is completed from Part A of C5351004, the original dose from Part A of C5351004 should be continued in C5351005. After the optimal efficacious dose is determined in C5351004, participants may have their dose adjusted to the optimal efficacious dose in C5351005.

If there is a delay in dosing for participants from Part A of the C5351004 study prior to entry into this OLE study, a modified loading dose will be administered depending on the dose received in the previous study as follows:

**Table 14. Modified Loading Dose for Those with a Gap in Treatment from C5351004 Part A, Part B, and Part C**

Amount of Consecutive Days with Missed Doses	100 mg Maintenance Dose	150 mg Maintenance Dose	200 mg Maintenance Dose
>3 to <7 consecutive days of missed doses	200 mg QD x 3 days	300 mg QD x 3 days	300 mg QD x 4 days
7 to <14 consecutive days of missed doses	200 mg QD x 5 days	300 mg QD x 5 days	300 mg QD x 7 days
14 to <42 consecutive days of missed doses	200 mg QD x 7 days	300 mg QD x 7 days	300 mg QD x 10 days
42 consecutive days of missed doses or greater	200 mg QD x 7 days	300 mg QD x 7 days	300 mg QD x 14 days

Abbreviations: BID, twice daily; QD, once daily.

## Dose for Participants Enrolled from Part B of C5351004

Table 15. Dose for Participants Enrolled from Part B of C5351004

Maintenance Dose in Part B of C5351004	Maintenance Dose in C5351005	Loading Dose in C5351005
150 mg dose or placebo	150 mg dose selected for Part B of C5351004	Not applicable

## Dose for Participants Enrolled from Part C of C5351004

Table 16. Dose for Participants Enrolled from Part C of C5351004

Maintenance Dose in Part C of C5351004	Maintenance Dose in C5351005	Loading Dose in C5351005
Participants will be administered a dose that provides generally equivalent exposure to 150 mg QD in adult SCD participants	Remain on the dose selected in Part C of C5351004	Not applicable

Abbreviations: TBD, to be determined.

## 11.4. Appendix 2: Liver Safety: Suggested Actions and Follow-Up Assessments

### 11.4.1. Drug-induced Liver Injury

Participants will be monitored for signs of drug-induced liver injury (DILI).

Potential events of DILI will be defined as meeting all of the following criteria (as specified in the Food and Drug Administration (FDA) Guidance for *Drug-Induced Liver Injury: Premarketing Clinical Evaluation 2009* [FDA, 2009]).

- ALT  $>4 \times$  ULN or aspartate aminotransferase (AST)  $>3 \times$  ULN
- No other reason can be found to explain the combination of laboratory value increases (eg, acute viral hepatitis; alcoholic and autoimmune hepatitis; hepatobiliary disorders; nonalcoholic steatohepatitis; cardiovascular causes; concomitant treatments)

Potential events of DILI will be reported as SAEs. All participants with potential DILI will be closely followed until abnormalities return to normal or baseline or until all attempts to determine resolution of the event are exhausted.

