#### **9.4.9. Drug-induced Liver Injury**

Participants will be monitored for signs of drug-induced liver injury (DILI).

Potential events of DILI will be defined as meeting all the following criteria (as specified in the FDA Guidance for *Drug-Induced Liver Injury: Premarketing Clinical Evaluation 2009* [FDA, 2009]).

Potential events of DILI will be reported as SAEs (Section 9.4.8). All participants with potential DILI will be closely followed until abnormalities return to normal or baseline or until all attempts to determine resolution of the event are exhausted.

See [Appendix 2: Liver Safety: Suggested Actions and Follow-Up Assessments](#) in the event of potential DILI.

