- Participants with AST/ALT and T bili baseline values within the normal range who subsequently present with AST OR ALT values  $\geq 3 \times \text{ULN}$  AND a T bili value  $\geq 2 \times \text{ULN}$  with no evidence of hemolysis and an alkaline phosphatase value  $< 2 \times \text{ULN}$  or not available.
- For participants with baseline AST OR ALT OR T bili values above the ULN, the following threshold values are used in the definition mentioned above, as needed, depending on which values are above the ULN at baseline:
  - Preexisting AST or ALT baseline values above the normal range: AST or ALT values  $\geq 2$  times the baseline values AND  $\geq 3 \times \text{ULN}$ ; or  $\geq 8 \times \text{ULN}$  (whichever is smaller).
  - Preexisting values of T bili above the normal range: T bili level increased from baseline value by an amount of  $\geq 1 \times \text{ULN}$  or if the value reaches  $\geq 3 \times \text{ULN}$  (whichever is smaller).

Because knowledge of the total and unconjugated bilirubin, may suggest the treatment assignment, these measurements will be redacted to the Investigator and monitored on a

regular basis by an unblinded team. Rises in AST/ALT and T bili separated by more than a few weeks should be assessed individually based on clinical judgment; any case where uncertainty remains as to whether it represents a potential Hy's law case should be reviewed with the sponsor.

The participant should return to the investigator site and be evaluated as soon as possible, preferably within 48 hours from awareness of the abnormal results. This evaluation should include laboratory tests, detailed history, and physical assessment.

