In addition to repeating measurements of AST and ALT and total bilirubin for suspected Hy's law cases, additional laboratory tests should include albumin, creatinine kinase, direct and indirect bilirubin, gamma-glutamyl transferase, PT/INR, eosinophils (%), and alkaline phosphatase. Consideration should also be given to drawing a separate tube of clotted blood and an anticoagulated tube of blood for further testing, as needed, for further contemporaneous analyses at the time of the recognized initial abnormalities to determine etiology. A detailed history, including relevant information, such as review of ethanol, acetaminophen/paracetamol (either by itself or as a coformulated product in prescription or over-the-counter medications), recreational drug, or supplement (herbal) use and consumption, family history, sexual history, travel history, history of contact with a jaundiced person, surgery, blood transfusion, history of liver or allergic disease, and potential occupational exposure to chemicals, should be collected. Further testing for acute hepatitis A, B, C, D, and E infection, total bile acids, liver imaging (eg, biliary tract), and collection of serum samples for acetaminophen/paracetamol drug and/or protein adduct levels may be warranted.

All cases demonstrated on repeat testing as meeting the laboratory criteria of AST/ALT and total bilirubin elevation defined above should be considered potential DILI (Hy's law) cases if no other reason for the LFT abnormalities has yet been found. **Such potential DILI (Hy's law) cases are to be reported as SAEs, irrespective of availability of all the results of the investigations performed to determine etiology of the LFT abnormalities.**

A potential DILI (Hy's law) case becomes a confirmed case only after all results of reasonable investigations have been received and have excluded an alternative etiology.

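### Two SAE-triggering definitions of potential DILI (11.4.1 and 11.4.2) are not nested and neither is said to govern; a combined rise with hemolysis at ALT 3× to 4× and AST no higher than 3× ULN meets neither

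*Protocol*

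**What the plan says.** Three protocol sections and one SAP section bear on this.

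- **Section 9.4.9** says "Potential events of DILI will be defined as meeting all the following criteria", lists none, makes potential DILI an SAE and refers to Appendix 2.
- **Section 11.4.1 (Appendix 2)** says "Potential events of DILI will be defined as meeting all of the following criteria". Two follow: ALT above 4× or AST above 3× ULN, and "No other reason can be found to explain the combination of laboratory value increases". Cases are SAEs. No bilirubin, alkaline phosphatase (ALP), hemolysis or baseline condition is listed.
- **Section 11.4.2 (Appendix 2)** requires, for normal baselines, AST or ALT at least 3× ULN and total bilirubin at least 2× ULN, "with no evidence of hemolysis and an alkaline phosphatase value" below 2× ULN or not available. For raised baselines, "the following threshold values are used in the definition mentioned above", so only the numbers change. Once repeat testing confirms the result and while no other reason has been found, such "cases are to be reported as SAEs, irrespective of availability of all the results of the investigations".
- **SAP 6.5.6** lists anyone with AST or ALT at least 3× and total bilirubin at least 2× ULN, with no hemolysis condition. It is a listing, not a reporting trigger.

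Section 11.4.2 also says that liver function tests are not routine in this study. Of total and unconjugated bilirubin it says "these measurements will be redacted to the Investigator", with an unblinded team monitoring them instead.

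**The concern.** Long-term safety is the primary objective, and SAP 6.1.1 tabulates treatment-emergent SAEs under it. Section 9.4.8 requires SAEs to be reported within 24 hours of awareness. With two definitions under one name and no statement of how they relate, the SAE flag and the start of that clock can depend on which subsection a site applies.

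The hemolysis condition adds a problem specific to this disease. The protocol describes SCD as characterized by hemolytic anemia, yet gives no marker or cutoff for evidence of hemolysis. The 11.4.2 work-up list names direct and indirect bilirubin but not LDH, reticulocytes or haptoglobin. Read literally, the condition can keep participants off the Hy's law route.

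The two other sentences do not fit the study. Tables 1 to 4 schedule serum chemistry repeatedly, and Table 9 includes ALT, AST, ALP and bilirubin in it. Section 7.3 says that blinding does not apply, and an Investigator without bilirubin cannot apply 11.4.2.

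**Working it through.** There is no plan figure to reproduce; the check is logical. All values are multiples of ULN.

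**Rules**

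- 11.4.1: (ALT > 4 or AST > 3) and no other reason.
- 11.4.2: (ALT or AST ≥ its threshold) and bilirubin ≥ its threshold and no hemolysis and ALP < 2 or unavailable.
- ALT/AST threshold: 3 if baseline is normal; otherwise min(max(2 × baseline, 3), 8).
- Bilirubin threshold: 2 if baseline is normal; otherwise min(baseline + 1, 3).

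**Two readings of 11.4.1 are open.** Hemolysis may or may not count as another reason. Because the text speaks of a combination of increases, a bilirubin line may be missing; I assume > 2 for that variant.

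**Eight profiles, not frequencies.** ALT 3.5 or 6; bilirubin 1 or 2.5; hemolysis yes or no. AST is 2.5, ALP below 2, baselines normal, results confirmed on repeat, no cause other than hemolysis. Section 11.4.2 is met by the two non-hemolytic profiles with bilirubin 2.5.

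| Reading of 11.4.1 | Meets 11.4.1 | Meets 11.4.2 | Rules disagree | Meets either | Combined rises (of 4) meeting neither |
|---|---|---|---|---|---|
| As written, hemolysis not a reason | 4 | 2 | 4 | 5 | 1 |
| Hemolysis is a reason | 2 | 2 | 2 | 3 | 2 |
| Bilirubin line assumed | 2 | 2 | 2 | 3 | 1 |
| Both | 1 | 2 | 1 | 2 | 2 |

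**Cases with the same answer under all four readings** (AST 2.5; unless stated, baselines normal, ALP below 2)

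- (a) ALT 3.5, bilirubin 2.5, no hemolysis: 11.4.2 only (3.5 is not > 4).
- (b) The same with hemolysis: neither.
- (c) Baseline ALT 2.5, now 4.5, bilirubin 2.5, no hemolysis: 11.4.1 only. The 11.4.2 threshold is 2 × 2.5 = 5.0.
- (d) Baseline bilirubin 1.8, now 2.5, ALT 6, no hemolysis: 11.4.1 only. The 11.4.2 threshold is 1.8 + 1 = 2.8.
- (e) ALT 6, bilirubin 2.5, ALP 2.5, no hemolysis: 11.4.1 only.

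Case (a) shows that 11.4.2 is not a subset of 11.4.1; (c) to (e) show that the reverse also fails.

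**The gap.** With hemolysis, 11.4.2 fails whatever the baseline; with ALT ≤ 4 and AST ≤ 3, 11.4.1 fails. A grid over that region (ALT 3 to 4, AST ≤ 3, bilirubin ≥ 2, hemolysis, normal and raised baselines) agrees: 0 of 2,880 combinations meet either rule, and all 2,880 enter the SAP listing. Without hemolysis, at normal baselines and ALP 1, all 80 of 80 meet 11.4.2. ALT 3 to 4 with ALP ≥ 2, or below a raised-baseline threshold, also meets neither rule, but those limits are explicit conditions of 11.4.2.

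**SAP screen.** The adjusted ALT/AST threshold is never below 3, and for a raised bilirubin baseline b > 1, min(b + 1, 3) exceeds 2. The 3×/2× screen therefore contains every 11.4.2 case, with or without the hemolysis condition.

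**The case against.** The strongest reply is that both sections order an SAE report, neither says only if, and nothing lets a site choose between them. A site complying with both reports (a), (c), (d) and (e). That stands, and leaves (b) as the gap. It does not remove the defect: 11.4.1 defines the term by its own full set of criteria, and no text says that either rule suffices.

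A reader might infer that gap cases go unreported. The documents do not support that. Section 9.4.2 lists drug-induced liver injury as an SAE outcome without laboratory thresholds and allows judgment on important medical events. Section 11.4.2 sends to the sponsor "any case where uncertainty remains as to whether it represents a potential" Hy's law case. Table 8 asks for repeat testing from ALT 3×, and for a hold above 3× with signs such as raised conjugated bilirubin or jaundice. SAP 6.5.6 lists the case. What is missing is a laboratory-defined trigger.

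A reader might also infer that 11.4.1 should give way to 11.4.2. That would remove the automatic trigger for (c), (d), (e) and isolated rises such as ALT 6×. Nor would deleting the hemolysis condition alone be enough: 11.4.2 also makes a case potential DILI only while no other reason has been found, and hemolysis could be read as one.

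On redaction, the unblinded team could apply the definition, and Section 3.3 foresaw entrants from blinded treatment. But all participants here receive osivelotor, and SAP 2.2.3 says that only Part A participants, whose treatment was open-label, were enrolled.

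**Conclusion.** The concern holds in this form: two non-nested SAE-triggering definitions, no statement of how they relate, a body section with no criteria, and one gap in hemolytic participants that persists even when either rule triggers a report. If hemolysis counts as another reason under 11.4.1, the gap extends above ALT 4×.

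The disagreement on 1 to 4 of 8 profiles shows that the regions exist; it says nothing about how often events fall in them. How often the hemolysis condition would block a report cannot be determined from the documents.

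The effect is limited to the SAE flag, its timing and the SAE tables. A reader might infer that the primary TEAE incidence is distorted. It is not, because Section 9.4.7.2 records clinically significant laboratory results as AEs anyway. With only Part A adults enrolled, protocol wording may reach few new events. It should still be fixed, since the change is nearly free and concerns safety reporting.

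**What to change.** 1. In 9.4.9 and Appendix 2, state that an event meeting either 11.4.1 or 11.4.2 is reported as an SAE. No current trigger is then lost, including raised-baseline cases and those with ALP at least 2×.
2. Remove absence of hemolysis as a reporting condition in 11.4.2. State that hemolysis alone is not another reason that delays a report under either section. Record it in the work-up using direct bilirubin, LDH and reticulocytes, all already collected under Table 9.
3. Delete the sentences saying that liver tests are not routine and that bilirubin is redacted.
4. In SAP 6.5.6, keep the 3×/2× screen and flag cases meeting the protocol definition. Print baseline and concurrent AST, ALT, ALP, total and direct bilirubin, LDH and reticulocytes. Isolated rises under 11.4.1 fall outside this screen and appear in the SAE tables.

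The cost is wording, one flag and a few listing columns, with no new tests, plus a few more SAE reports in participants with hemolysis. On the eight profiles, with 11.4.1 as written, reports under either rule go from 5 to 6: the four with ALT 6 plus both with ALT 3.5 and bilirubin 2.5. If hemolysis is now read as another reason, they go from 3 to 6. The SAP change can be made whatever happens to the protocol.
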